7.2.3. Expectedness of Event

The Principal Investigator or qualified designate will also assess all recorded adverse events on basis of event severity, frequency (if applicable/assessable), and the established product risk information described within the product Investigator's Brochure; the FDA-approved product labeling (if an approved agent); and/or this protocol document, as to whether the events are "expected" or "not expected" relative to the study interventions and/or the study / procedures.

Note that unexpected adverse events may have reporting requirements as described elsewhere in this section.

7.2.4. Time Period of Event Assessment and Follow-up

Adverse events will be recorded from the time the subject signs the informed consent form and for 30 days after the last study treatment, except if being monitored for a related adverse event.

If a subject is removed from study due to unacceptable adverse event(s) toxicity, that subject will be followed & safety data collected for at least 30 days and until resolution or stabilization of the adverse event, to the extent possible. All SAEs will be followed for 30 days after the last dose of study treatment, or until the SAE(s) is/are resolved or stable, whichever is longer. Pregnancies will be followed until term. See also Sections 3.8, 5.6, 6.0, and 7.6.

7.3. Potential Adverse Events and Risks

A brief summary of nirogacestat adverse events and risks was described in Section 1.3.1 Known Potential Risks.

In addition to the summary risks described in Section 1.3.1, adverse events described by severity and frequency within the research agent nirogacestat Investigator's Brochure and/or the Ogsiveo™ (nirogacestat) package insert are considered anticipated, ie, not unexpected. Procedural risks described in Section 1.3.1 are considered anticipated.

Cryoablation is widely used within the Stanford Cancer Institute for the treatment of cancer, both as an individual treatment as well as part of a treatment regimen, and its risk profile is well understood as a regular medical care procedure. Risks associated with cryoablation are expected in accordance with the current FDA 510k approval. It is not known if there are additional risks of cryoablation in combination with the study drug, nirogacestat. However, safety is being monitored, as described within this section and within Section 6.2.2 (Safety and Other Assessments). Doses of nirogacestat may be adjusted in response to specific adverse events, as described in Section 5.6 (Dose Modifications).

7.3.1. **Nirogacestat** (Information from Investigator's Brochure)⁴ Please also reference the Ogsiveo™ (nirogacestat) package insert.²⁸

Special Warnings and Precautions for Use

To date, important identified risks related to nirogacestat include diarrhea, dermatologic reactions (maculopapular rash, hidradenitis, and folliculitis), ovarian dysfunction, electrolyte abnormalities (hypophosphatemia and hypokalaemia), and elevated liver transaminases. Important potential risks include non-melanoma skin cancer (basal cell carcinoma and squamous cell carcinoma), embryo-fetal toxicity, effects on male fertility, and in pediatric patients, epiphyseal disorder.

- **Diarrhea**

Nonclinical data suggest that inhibition of GS may interfere with the integrity of the lower gastrointestinal tract epithelium and control of intestinal motility. GS inhibition may affect the intestinal tract epithelium (Barker, 2007; Kurokawa, 2020), villus lacteals (Norden, 2021), and enteric nervous system (Willem, 2016; Barrenschee, 2015), and lead to diarrhea.

In the Study NIR-DT-301, diarrhea occurred in 84% of participants who received nirogacestat compared to 35% in participants given placebo. Grade 3 events occurred in 16% of participants; no events of Grade 4+ diarrhea were reported. Participants should be monitored and diarrhea managed according to recommendations in Section 5.6 Dose Modifications.

- **Dermatologic reactions**

The Notch signaling pathway exerts a crucial role in regulating and maintaining skin homeostasis, orchestrating keratinocyte differentiation at the level of inter-follicular epidermis and hair follicles, and finally working in epithelial barrier formation (Condorelli, et al, 2021). Further, a genetic association between mutations in the GS complex and hidradenitis suppurativa has been described in the literature (Wang 2010; Frew et, 2017). In addition, when GS is inhibited, the outer root sheath cells activate epidermal differentiation which results in the conversion of hair follicles to cysts (Melnik B, Plewig G, 2013).

Nirogacestat can cause dermatologic reactions including maculopapular rash (32%), hidradenitis (9%), and folliculitis (13%). Participants should be monitored for skin reactions throughout the treatment course and managed as clinically indicated. See Section 5.6 Dose Modifications.

- **Ovarian Dysfunction:**

Nonclinical data for nirogacestat showed ovarian atrophy with decreased follicular development and no presence of corpora lutea at clinically relevant doses in rats. GS inhibition may interfere with both the angiogenesis needed to support luteal development (Vanorney, et al, 2017) and the cell-to-cell signaling within the thecal cell layer to control luteal development (Hahn, et al, 2005; Zhang C-P, et al, 2011).

In Study NIR-DT-301, 75% of WOCBP receiving nirogacestat reported events related to OD. The median time to first onset of OD was 8.9 weeks and the median duration of events was 21.3 weeks. These events resolved in 64% of WOCBP with OD who continued taking nirogacestat and in all WOCBP who stopped nirogacestat for any reason. OD events are accompanied by suppression of AMH and estradiol production, and increases in FSH, LH, and progesterone; however, nirogacestat treatment did not appear to result in a prolonged suppression of estradiol. Effects of nirogacestat on fertility are unknown. WOCBP should be advised about the risk of OD before initiating treatment with nirogacestat.

- **Electrolyte Abnormalities:**

GS inhibition may affect the intestinal tract epithelium (Barker, 2007; Kurokawa, 2020), villus lacteals (Norden, 2021), and enteric nervous system (Willem, 2016; Barrenschee, 2015), and lead to diarrhea, which could in turn lead to loss of electrolytes. In addition, Notch signaling in the nephron is responsible for the maintenance of the balance of epithelial cell type diversity and epithelial repair (Mukherjee, Fogarty, et al, 2019), and

disruption of this balance could lead to altered ability of the kidney to adapt to impaired electrolyte imbalances (Mukherjee, deRiso, et al., 2019).

Electrolyte abnormalities occurred in participants taking nirogacestat in Study NIR-DT-301. This included hypophosphatemia (42%) and hypokalemia (12%). Grade 3 events occurred in 3% and 1% of participants, respectively. Phosphate and potassium levels should be monitored regularly and supplemented as necessary. See also Section 5.6 Dose Modifications.

- **Elevated Liver Transaminases:**

Effects on hepatic function emerged as an AE of special interest for nirogacestat based on observations of mild hepatic vacuolation in nonclinical studies in rats, and transient transaminase elevations in early clinical studies with nirogacestat.

ALT or AST elevations occurred in 20% of participants who received nirogacestat in Study NIR-DT-301. Grade 3 ALT or AST elevations (> 5 times ULN) occurred in 3% of participants. The majority of ALT or AST elevations were Grade 1 (> ULN to 3 times ULN), occurred within the first month of treatment, and resolved spontaneously without dose modification. Liver function tests should be monitored regularly. See Section 5.6 Dose Modifications and Section 13.8 Appendix G Liver Safety: Suggested Actions and Follow-up Assessments.

- **Embryo-fetal Toxicity:**

Based on its mechanism of action and data from animal studies, nirogacestat may cause fetal harm when administered to a pregnant woman. In animal reproduction studies, administration of nirogacestat to rats during organogenesis resulted in embryo loss, resorption and decreased fetal weights in surviving embryos, while administration of nirogacestat to rats prior to conception resulted in decreased early embryo-fetal implantation and early embryonic loss. These effects occurred at exposures below those occurring clinically at the recommended dose. Advise patients of the potential risk to a fetus. Advise women of childbearing potential to inform their healthcare provider of a known or suspected pregnancy, and to stop taking nirogacestat if they become pregnant. Advise women of reproductive potential to use effective contraception during treatment with nirogacestat and for 1 week after the last dose. Advise male patients with female partners of reproductive potential to use effective contraception during treatment with nirogacestat and for 1 week after the last dose. Women should not donate or harvest their eggs (ova, oocytes) while participating in this research study and for at least 6 months after taking their last dose of study drug. Men should not donate or preserve their sperm for at least 90 days after taking their last dose of study drug.

- **Effects on Male Fertility:**

In the 3-month dog study, changes in the testes include vacuolation of Sertoli cells, degenerative spermatids and loss of spermatocytes and germinal cells were observed. In the treated male rats, a decrease in epididymal weight was noted. Sperm motility was markedly lower at all dose levels, and mean cauda epididymal sperm concentrations

were lower in the 20 and 40 mg/kg/day groups when compared to the control group. In addition, the percentages of morphologically normal sperm in the 20 and 40mg/kg/day groups were lower than the control group.

- **Epiphyseal Disorder:**

Increased retention of the hypertrophic zone of the growth plate and articular cartilage (sternum and joint) was seen at >20 mg/kg/day in the 1-month study rat study. This change was characterized by minimal to moderate thickening of the hypertrophic zone in the cartilage with pallor and slight vacuolation of the osteocytes in the primary spongiosa. Partial recovery of these effects were evident after discontinuation of nirogacestat. This response is similar to those observed with vascular endothelial growth factor (VEGF) inhibitors. Whether the anti-angiogenic like effects of nirogacestat are mechanism-related (i.e., a result of Notch inhibition or effects on other GS substrates) or are downstream effects on angiogenic growth factor signaling (i.e., VEGF) cannot be determined at this time.

Events of limb asymmetry, slipped capital femoral epiphysis, epiphyseal disorder, femoral neck fracture, and osteonecrosis of the femoral head have been reported by pediatric patients participating in the nirogacestat compassionate use and the investigator-initiated research program. Routine growth plate monitoring of the tibial growth plate has been included in clinical trials involving participants with open growth plates. Participants with open growth plates being treated with nirogacestat should have their tibial growth plate monitored. Nirogacestat should be discontinued if fracture through an open growth plate or osteonecrosis are observed.

- **Reproductive System Effects:**

- **Pregnancy:**

Pregnant women will be excluded from participation in this clinical study with nirogacestat. Study participants will be required to utilize highly effective contraception and avoid pregnancy while receiving nirogacestat. If a subject becomes pregnant while receiving nirogacestat, the treatment with nirogacestat should be stopped, and the subject will be apprised of the potential hazard to the fetus.

Women of childbearing potential must have a negative pregnancy test prior to starting treatment with nirogacestat and must agree to use a highly effective method of contraception (ie, copper-containing intrauterine device, established use of oral, injected or implanted hormonal method of contraception, or male/female sterilization) while receiving treatment with nirogacestat and for at least 1 week after the last dose of active study treatment. A second method of contraception is required if the female subject is using hormonal contraception, as coadministration with nirogacestat may result in reduced plasma concentrations of hormonal contraceptives and increase the risk of reduced efficacy. See also Appendix H.

If a pregnancy is reported, the investigator will inform SpringWorks within 72 hours of learning of the pregnancy by completing a Stanford SAE form and submitting to Safety ([contact]).

Abnormal pregnancy outcomes (e.g., spontaneous abortion, fetal death, stillbirth, congenital anomalies, ectopic pregnancy) are considered SAEs.

Male subjects must use a condom when having sexual intercourse with a woman of childbearing potential (WOCBP) while receiving treatment with nirogacestat and for at least 1 week after the last dose. An additional form of highly effective contraception should also be used by the female partner, if of childbearing potential.

Women should not donate or harvest their eggs (ova, oocytes) while participating in this research study and for at least 6 months after taking their last dose of study drug. Men should not donate or preserve their sperm for at least 90 days after taking their last dose of study drug.

Lactation: No studies have been conducted in humans to assess the impact of nirogacestat on milk production, its presence in breast milk and its effects on the breast-fed child. Since drugs are commonly excreted in human milk and because of the potential for serious adverse reactions in nursing infants, breastfeeding women should not receive nirogacestat administration.

Effects on Ability to Drive and Use Machines:

The effects on the ability to drive or operate machinery or impairment of mental ability have not been formally studied with nirogacestat. No Grade 3 events that might be associated with an effect on the ability to drive machinery occurred at an incidence of >1% in any single-agent study among all participants receiving any dose of nirogacestat. Based on these data, nirogacestat is not expected to have a clinically significant effect on the ability to drive or operate machinery.

Summary of the Most Commonly (≥ 10% of Participants in the Nirogacestat Arm) Reported AEs from Completed Nirogacestat Single Agent Studies in Adult Patients with Cancer (Modified Information from Investigator's Brochure)*⁴ Please also reference the Ogsiveo™ (nirogacestat) package insert.²⁸

- Diarrhea
- Fatigue
- Hypophosphatemia
- Cough
- Rash maculo-papular
- Rash
- Headache
- Dry mouth
- Dermatitis acneiform
- Nausea
- Vomiting
- Decreased appetite
- Pyrexia
- Hypokalemia
- Aspartate aminotransferase increased
- Epistaxis
- Alanine aminotransferase increased
- Abdominal pain

- Insomnia
- Stomatitis
- Dyspnea
- Anemia
- Constipation
- Upper respiratory tract infection
- Hot flush
- Arthralgia
- Dry skin
- Dizziness
- Hypertension
- Pruritus

*Data from Single Agent Nirogacestat Studies A8641014, A8641020, 14-C-0007, and NIR-DT-301 (Double-Blind Phase).

Table 6. Adverse Reactions Reported in at Least 15% Patients and at a $\geq 5\%$ Rate in the Nirogacestat Arm Than the Placebo Arm in NIR-DT-301 (Modified Information from Investigator's Brochure)⁴ Please also reference the Ogsiveo™ (nirogacestat) package insert.²⁸

Adverse Reaction	Nirogacestat (N=69)		Placebo (N=72)	
	All Grades n (%)	Grade 3* n (%)	All Grades	Grade 3* n (%)
Reproductive system				
Ovarian dysfunction ^a	27 (75%)	0	0	0
Skin and subcutaneous tissue				
Rash ^b	44 (64%)	4 (6%)	10 (14%)	0
Alopecia	13 (19%)	0	1 (1%)	0
General				
Fatigue	35 (51%)	2 (3%)	26 (36%)	0
Nervous system				
Headache	20 (29%)	0	11 (15%)	0
Respiratory				
Cough	11 (16%)	0	3 (4%)	0
Dyspnea	11 (16%)	0	4 (6%)	0
Infections				
Upper respiratory tract infection ^c	11 (16%)	0	1 (1%)	0
Metabolism				
Hypophosphatemia	29 (42%)	2 (3%)	5 (7%)	0
Investigations				
ALT increased	12 (17%)	2 (3%)	6 (8%)	1 (1%)
AST increased	11 (16%)	2 (3%)	8 (11%)	1 (1%)

* No Grade 4 or 5 adverse reactions were reported in Study NIR-DT-301.

^aOvarian dysfunction includes Ovarian failure, Premature menopause, Amenorrhea, and Menopause; the number of women of childbearing potential in each arm is used as the denominator (nirogacestat N=36, placebo N=37),

^bRash includes Maculo-papular rash, Dermatitis acneiform Rash , Rash erythematous , Rash pruritic , and Rash papular .

^cUpper respiratory tract infection (URTI) includes URTI, Viral URTI, Acute sinusitis, and Sinusitis

Premature Menopause / Ovarian Dysfunction

- In the Phase 3 Study NIR-DT-301 evaluating nirogacestat in adult patients with progressing desmoid tumors, ovarian dysfunction, which was defined by investigator-reported events of amenorrhea, premature menopause, menopause, and ovarian failure, was observed in 75% (27/36) of women of childbearing potential receiving nirogacestat and none of the 37 women of childbearing potential in the placebo arm. All ovarian dysfunction events were Grade 2. These events resolved in 74% (20/27) of the affected participants, including 64% (9/14) of such participants who remained on nirogacestat treatment and 100% (11/11) of those participants who discontinued treatment for any reason.²⁷

Important Side Effect of Nirogacestat Occurring in < 10% of Participants:

- Non-melanoma skin cancer*

*Non-melanoma skin cancer includes Basal cell carcinoma [1 (1%)], Squamous cell carcinoma of skin [2 (1%)], and Squamous cell carcinoma [1 (1%)].

Summary of TEAEs in Phase 2 Study of Nirogacestat 150 mg Twice-daily in 17 Subjects with Desmoid Tumors, Study WI180798 (NCT01981551) (Modified Information from Investigator's Brochure).⁴ Please also reference the Ogsiveo™ (nirogacestat) package insert.²⁸

- Most frequently reported TEAEs:
 - Diarrhea (88%)
 - Headache (76%)
 - Hypophosphatemia (76%)
 - AST increased (71%)
 - Lymphocyte count decreased (71%)
 - Nausea (71%)
- Additional reported TEAEs in Study WI180798
 - Diarrhea Grade 3 (1 [6%] subject)
 - Fatigue Grade 3 (1 [6%] subject)
 - Menstruation irregular Grade 3 (1 [6%] subject; subject was postmenopausal prior to enrolling in the study, and per study sponsor this event should not have been reported as a TEAE)
 - Hypophosphatemia Grade 3 (8 [47%] subjects)
- SAEs reported in Study WI180798: 4 SAEs were considered related to nirogacestat by the investigator, and each SAE was reported in a single patient. All were reported as Grade 2 severity. There was one death due to a cerebrovascular accident that was

assessed by the investigator as unlikely related to nirogacestat. There were no TEAEs that were considered to be DLTs.

- Blood bilirubin increased
- Hypersensitivity – led to permanent discontinuation of study treatment in one patient.
- Squamous cell carcinoma
- Vulvovaginal inflammation

Other AEs

- Anaphylactic shock
- Cholecystitis (Reported in ongoing NIR-DT-301 study in less than 1% of study participants)
- Arrhythmia

Table 7. Serious Adverse Drug Reactions for Nirogacestat Considered Expected for Safety Reporting Purposes: Please see Investigator's Brochure Reference Safety Information (RSI) section. The RSI outlines expected serious adverse reactions for regulatory reporting purposes.

Known Drug Interactions:

Modified information from nirogacestat Investigator's Brochure ⁴; See also Section 3.1.3. (Lifestyle Considerations), and Section 1.3 (Potential Risks and Benefits), and Appendix F. Please also reference the Ogsiveo™ (nirogacestat) package insert.²⁸

- **Cytochrome P450 Inhibitors and Inducers** (from Investigator's Brochure) ⁴
 - Coadministration of nirogacestat with strong or moderate inhibitors of CYP3A4 may increase serum nirogacestat concentrations and should be avoided. The use of strong or moderate CYP3A4 inhibitors must be stopped at least 14 days prior to the first dose of study treatment. If coadministration of strong or moderate CYP3A4 inhibitors is unavoidable, immediately interrupt nirogacestat treatment and remain off nirogacestat for the period of time that the CYP3A4 inhibitor is given. Nirogacestat may be resumed one week after cessation of a strong CYP3A4 inhibitor and immediately following cessation of a moderate CYP3A4 inhibitor.
 - Nirogacestat metabolism may be induced when taking strong CYP3A4 inducers resulting in reduced nirogacestat serum concentrations. The use of strong CYP3A4 inducers must be stopped at least 14 days prior to the first dose of study treatment. Co-administration of nirogacestat with strong CYP3A4 inducer should be avoided. If a strong CYP3A4 inducer is required, nirogacestat may be interrupted for the period of time that the CYP3A4 inducer is given and may be resumed immediately after cessation of the CYP3A4 inducer. Dose modifications are not recommended if a moderate CYP3A4 inducer is required.

- **Cytochrome P450 Substrates**

- Nirogacestat is a weak inhibitor of CYP3A4 at therapeutic doses and may increase the exposure of drugs that are metabolized by CYP3A4. Concomitant use of nirogacestat with CYP3A4 substrates that have a narrow therapeutic index should be avoided.
- Based on the potential for increased exposure on co administration with nirogacestat, CYP3A4 substrates with a narrow therapeutic index should be avoided if possible. If co-administration is unavoidable, the participant should be monitored closely for toxicity and investigator should consider reducing or titrating the dose of the substrate as necessary.
- Based on physiologically-based pharmacokinetic (PBPK) model predictions, nirogacestat may be a weak-to-moderate inducer of CYP2C19 and may reduce the exposure of drugs that are metabolized by CYP2C19. Therapeutic alternatives to CYP2C19 substrates should be considered as appropriate, however strict avoidance of concomitant use with nirogacestat is not necessary.

- **Other Concomitant Therapy**

- The effect of nirogacestat on the exposure of hormonal contraceptives has not been evaluated. However, induction of these CYP enzymes has been associated with reduced plasma exposure of various hormonal contraceptives resulting in reduced efficacy.
- Nirogacestat is a substrate for the drug efflux transporter P-glycoprotein (P-gp). Caution should be used when co-administering the nirogacestat with known P-gp inhibitors such as amiodarone, azithromycin, captopril, carvedilol, elacridar, felodipine, mibepradil, nitrendipine, quinidine, ranolazine, talinolol, and valsopdar. Nirogacestat may also be an inhibitor of P-gp and may increase the exposure of some P-gp substrates like digoxin, dabigatran, and fexofenadine; participants receiving these medications should be closely monitored, as therapeutic effect and adverse reactions of these medications may be increased.
- Gastric acid reducing agents: Based on the solubility characteristics of nirogacestat, increase of gastric pH may reduce absorption of nirogacestat, although the extent of the effect has not been evaluated in a clinical study. Daily use of gastric acid reducing agents should be avoided. If gastric acid reducers are required, they should be administered 4 hours after administration of nirogacestat.

7.3.2. Cryoablation

The risks of ablation include but are not limited to ecchymosis, edema/swelling, fever, hemorrhage, infection, delayed/non-healing wound, pneumothorax, probe site paresthesia, skin burn, and injury to off-target structures. With any procedure there is a small risk of death.

Based on CRYODESMO-01, Grade 1 and 2 toxicity occurred in 32.8% and 44.5% of subjects, Grade 3-4 toxicity occurred in 22% of subjects, and no Grade 5 toxicity was observed. The most common side effects included:¹⁶

- Pain (21.6%)
- Neural impairment (15.8%)
- Edema (15.1%)
- Musculoskeletal impairment (7.9%)
- Skin burn (5.8%)
- Increased creatinine kinase (5.8%)
- Bleeding (2.9%)
- Fever (0.7%)

7.4. Adverse Event Monitoring and Collection

Untoward medical events experienced by a study subject receiving an interventional drug, device, or procedure, or within **30** days after such treatment, will be considered an adverse event (AE), regardless of whether or not considered drug-related. All events of disease progression or second cancer will be recorded as a serious adverse event (SAE) using the Preferred Term appropriate for the clinical finding.

All adverse events Grade 1 and higher will be collected and recorded as AEs.

In addition, laboratory values without a requirement for intervention, clinical consequence, or outcome will not be considered adverse events, unless deemed serious.

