7.1. Adverse Event Definitions

An adverse event is any untoward medical occurrence associated with the use of a drug in humans, whether or not considered drug-related. An adverse event can be any unfavorable and unintended sign or symptom, including abnormal laboratory findings, or disease, that is temporally associated with the use of a drug, and does not imply any judgment about causality. An adverse reaction is any event that is caused by a drug or device, ie, possibly-, probably-, or definitely-related to the use of the drug or device.

Except as otherwise explicitly defined within this section, **this also includes all events of clinical deterioration such as tumor relapse, recurrence, or upstaging, or new cancers.**

Within the scope of this study and protocol, adverse device effects, ie, events that have a serious adverse effect on health or safety or any life-threatening problem or death caused by, or associated with, a device may be referred to as "serious adverse events (SAEs)."

Serious adverse events (SAEs) are defined per the FDA definition at [21CFR§312.32\(a\)](#) and [ICH GCP E6](#). An adverse event is considered "serious" if, in the opinion of the PD, investigator, or sponsor, it results in ANY of the following.

- Death
- Life-threatening adverse event with an **actual and immediate risk of death** [21CFR§312.32(a)]
- In-patient hospitalization or prolongation of existing hospitalization, except planned hospitalization or hospitalization only for study conduct will not be considered SAEs. Note that the per-protocol cryoablation procedure will not be considered an SAE hospitalization, even if the patient stays in the clinic overnight.
- A persistent or significant incapacity or substantial disruption of the ability to conduct normal life functions
- A congenital anomaly/birth defect
- Event jeopardizes the subject and may require medical or surgical intervention to prevent one of the outcomes listed here

7.2. **Classification of Adverse Events**

7.2.1. **Severity of Event**

NCI CTCAE version 5.0 is used to assess the severity of adverse events in this study.

7.2.2. **Adverse Event Attribution to Intervention or Study**

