7.5. Adverse Events of Special Consideration

7.5.1. Second vs Secondary Malignancy

7.5.1.1. Second Malignancy

A second malignancy is one unrelated to the treatment of a prior malignancy (and is NOT a metastasis from the initial malignancy). A second malignancy is by definition a serious adverse event (SAE), and will be recorded and reported accordingly.

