7.5.2. Progressive Disease

Progressive disease will be reported by the clinical signs or symptoms of disease progression. If the event is Grade 5 fatal and signs/symptoms of disease progression are not available / informative for the event, the CTCAE v5.0 preferred term "Disease Progress" may be used.

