7.5.3. Other Adverse Events of Special Interest

Adverse events of special interest (AESI) are selected non-serious and serious AEs that must be reported regardless of relationship to study treatment. Refer to Table 8 for the AESIs identified for this study. AESIs will be followed until resolution or return to baseline.

Serious AESIs will be reported to SpringWorks Safety at ([contact]) according to procedures and timeline (Section 7.6)

Non-serious AESIs must be reported to SpringWorks Safety at [contact] as soon as possible, but no later than 30 calendar days of awareness.

Following medical evaluation, SpringWorks may request study site to provide supplemental information (such as medical history, concomitant medications, investigations, etc.) about the event. Please note this table lists known AESI; additional events may be identified during the course of the study.

Table 8. Adverse Events of Special Interest

Elevated Liver Enzymes (reported as AESI if Grade ≥ 2, per CTCAE v. 5)

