1. AST
2. ALT
3. Alkaline Phosphatase
4. Total bilirubin
Drug Reactions, any Grade
1. Allergic reaction
2. Anaphylaxis
3. (Drug) Hypersensitivity
Ovarian Dysfunction, any Grade¹
1. Ovarian dysfunction
2. Ovarian Disorder
3. Amenorrhea
4. Oligomenorrhea
5. Premature Menopause
6. Ovarian failure
Non-Melanoma Skin Cancer, any Grade, and Pre-cancerous Skin Lesions, any Grade
1. Basal cell carcinoma
2. Squamous cell carcinoma (of skin)
3. Keratoacanthoma
4. Actinic keratosis

¹ Females reporting AEs / AESIs / SAEs of ovarian dysfunction will have hormone levels assessed every 3 months until event resolution (or for at least 90 days after discontinuing study treatment).

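### Section 7.4 makes every disease progression a serious adverse event, against the outcome-based definition in 7.1, so symptom-free failures of the primary endpoint enter the SAE listings

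*Protocol*

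**What the plan says.** Five parts of the Protocol bear on this.

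- **Section 7.4**: "All events of disease progression or second cancer will be recorded as a serious adverse event (SAE", coded with a preferred term that suits the clinical finding. No outcome is required and no progression criterion is named.
- **Section 7.1**: "Serious adverse events (SAEs) are defined per the FDA definition at" the cited federal regulation and ICH GCP. It then lists the qualifying outcomes: death, immediate threat to life, hospitalization, lasting incapacity, birth defect, or an event that may need intervention to prevent one of these. The same section counts "all events of clinical deterioration such as tumor relapse, recurrence, or upstaging, or new cancers" as adverse events, without making them serious.
- **Section 7.5.2**: "Progressive disease will be reported by the clinical signs or symptoms of disease progression". The dedicated Disease Progress term is allowed only for a fatal event whose signs or symptoms are unavailable or uninformative.
- **Section 7.6**: three routes, worded differently. The 24-hour report to the sponsor-investigator covers SAEs under the 21CFR312.32 definition. The DSMC report covers SAEs without qualification. The IRB continuing-review report covers SAEs as the protocol defines them.
- **Sections 2.3.2.1 and 10.2.1.1**: the primary endpoint is clinical benefit at 1 year by RECIST v1.1, and a progression within that year is a failure.

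**The concern.** Section 1.2.1 describes a tumor that does not metastasize, and Section 6.1 schedules MRI every 12 weeks. A subject can therefore meet the 20% diameter threshold on a routine scan with none of the outcomes in 7.1. Such an event is serious under 7.4 and not serious under 7.1, and 7.6 does not say which section governs its reporting.

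The same event is also an efficacy failure. If it is listed as an SAE, the SAE listing rises and falls with efficacy. Section 9.3.1 has the DSMC regularly review SAEs and deviations. Section 7.3 says it is not known whether cryoablation carries added risks in combination with nirogacestat. Endpoint events would sit among the drug and procedure events that this review is meant to detect.

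**Working it through.** The Protocol gives no expected SAE count, so there is no figure to reproduce. The check is mainly textual, with arithmetic only for scale.

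**Textual check.** Take a subject without symptoms whose scheduled MRI shows a 20% increase in target-lesion diameter that qualifies as progression.

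1. Section 7.1: no listed outcome has occurred, so the event is not serious.
2. Section 7.4: it is a progression, so it is recorded as an SAE.
3. Section 7.5.2: it is to be reported by signs or symptoms. There are none, and the dedicated progression term is limited to fatal events.
4. Section 7.6: the event is outside the 21CFR312.32 definition, so the 24-hour route does not clearly apply. It is an SAE as the protocol defines it, so the IRB route does. The DSMC route, written for SAEs without qualification, is open to either reading.
5. Criterion: Section 10.2.2.2 assesses progression by RECIST v1.1, mRECIST and MRI volume, and 7.4 does not choose. Appendix E applies the RECIST degree of change to volume. With growth equal in all directions, a 20% volume increase is a diameter increase of 1.2^(1/3) − 1 = 6.3%. Read literally, 7.4 could make that an SAE as well.

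**Inputs for scale.**

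- Evaluable subjects: 20, from up to 23 enrolled (Section 10.4.1).
- Clinical benefit rate: 0.8 under the alternative, 0.5 under the null (Section 10.4.2).
- Subjects with an SAE on nirogacestat: 14/69 = 20% in the phase 3 study and 9/17 = 53% in the phase 2 desmoid study (Section 1.2.4; the 69 is in Table 1).

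**Progression SAEs in year 1** = n × (1 − CBR), assuming that every failure is a progression.

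| CBR | n = 20 | n = 23 | P(at least one), n = 20 |
|---|---|---|---|
| 0.8 | 20 × 0.2 = 4 | 4.6 | 1 − 0.8^20 = 0.988 |
| 0.5 | 20 × 0.5 = 10 | 11.5 | 1 − 0.5^20 > 0.999 |

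**Other SAEs, n = 20**: 20 × 14/69 = 4.06 subjects, or 20 × 9/17 = 10.59 subjects.

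**Progression share, no overlap** = progression / (progression + other).

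| | Other SAEs at 14/69 | Other SAEs at 9/17 |
|---|---|---|
| CBR 0.8 | 4 / 8.06 = 50% | 4 / 14.59 = 27% |
| CBR 0.5 | 10 / 14.06 = 71% | 10 / 20.59 = 49% |

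The last cell sums to slightly more than 20 subjects, so a little overlap is unavoidable there and 49% is approximate.

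**The case against.** The strongest reply is that a protocol may define SAEs more widely than the regulation does, that doing so is cautious, and that 7.1 allows for exceptions defined elsewhere in the section. That allowance, however, belongs to the sentence on adverse events, not to the SAE definition. Even if a wider rule was intended for progression, 7.6 does not carry it through to the reporting routes.

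A second reply is that 7.4 asks for a term fitting the clinical finding and 7.4.1 permits a diagnostic term, so a site could enter something. This is fair: a term can be found. The Protocol simply does not assign one to a non-fatal progression seen only on MRI.

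A third reply is that the arithmetic leans high, and much of this stands. The null rate of 0.5 comes from subtotal cryoablation without nirogacestat (Section 10.4.3). The phase 2 nirogacestat study saw no progression. No SAEs from cryoablation are added to the comparison.

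Two stronger readings are tempting, and the documents do not support them.

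- **Distorted safety results.** A reader might infer that progressions would dominate the trial's safety results. Section 10.2.2.6 tabulates adverse events by grade, severity, status and relationship, and the registered outcome in Section 2.3.2.2 counts related events of Grade 3 or higher. Neither is an SAE count. No stopping rule uses one, and expedited IND reports still require an unexpected event at least possibly related to the drug.
- **Conflict over skin cancers.** Table 8 lists "Non-Melanoma Skin Cancer, any Grade, and Pre-cancerous Skin Lesions, any Grade", and a reader might infer that 7.5.3 treats skin cancers as non-serious. It does not: "Adverse events of special interest (AESI) are selected non-serious and serious AEs that must be reported regardless of relationship to study treatment", and Table 8 assigns no seriousness. Section 7.5.1.1 agrees with 7.4: "A second malignancy is by definition a serious adverse event (SAE), and will be recorded and reported accordingly". Nor do the 24-hour and 30-day limits conflict, since the first runs to the sponsor-investigator and the second to the drug supplier.

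**Conclusion.** The point holds for disease progression. Section 7.4 applies no outcome test, 7.1 requires one, 7.5.2 fits neither a symptom-free nor a non-fatal radiographic progression well, and 7.6 leaves the routes open. Primary-endpoint failures would therefore be listed as SAEs.

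On the design's own rates, that is about 4 to 10 of 20 subjects in year 1, or between 27% and 71% of subjects with an SAE across the four combinations. This rests on three assumptions: every failure of clinical benefit is a progression, progression SAEs and other SAEs fall in different subjects, and the quoted nirogacestat SAE rates carry over. The Protocol does not say how progression was classified in those studies. It also gives no figure for the share of progressions that would meet 7.1 anyway, which could be anywhere from none to all. Progressions in the second year would add to the count.

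The consequence is limited to the SAE listings and what the DSMC and IRB see through them. The change should be made, but the planned safety tabulation and the registered outcome do not depend on it.

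**What to change.** Reconcile Sections 7.1, 7.4, 7.5.2 and 7.6:

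1. In 7.4, record progression alone as an efficacy endpoint under one named criterion, RECIST v1.1.
2. State that a sign, symptom or outcome accompanying progression is an adverse event, serious only if it meets 7.1, and align 7.5.2 with this.
3. In 7.6, say for each route whether it covers SAEs under the regulation or the protocol's wider set.
4. List any SAE due to progression separately from other SAEs.

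Leave the second-malignancy rule in 7.4 and 7.5.1 as it is; it is stated consistently and nothing here argues against it.

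The cost is amendment wording and a CRF instruction, and it should reduce SAE paperwork. The small downside is that the DSMC would see progression through the efficacy listing instead of through SAE reports, so that listing should be given to it.
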